4.2. Operationalization

Randomization

This study will use cluster randomization, with each week group described as a cluster. Prior studies have investigated induction of labor methods utilizing cluster randomization. Cluster randomization will be computer generated and will assign each cluster (weeks) to the control or study group. Both the study group and the control group are considered part of the standard of care for induction of labor at UTMB. Clusters will be block randomized in groups (weekly).

Labor and Delivery Unit/Staff

Several training sessions will occur to notify all staff of the trial and the protocol. Training sessions will include a copy of the protocol to review as well as follow-up email communication. The PI will also be available for questions. All operations will be also reviewed with all staff.

At shift change 0630-0700 am and pm every Monday to Friday, randomization assignments will be announced to all nurses and providers on the Labor and Delivery unit. All staff caring for subjects during the week of randomization will be notified of the cluster randomized for that week for all labor inductions. Notifications and plastic tags will be placed in the workstations for the providers and at all nursing stations on labor and delivery and at the patient's room door stating Tension or No Tension. A notification will also be placed at the work station of the study team. All study team in the Perinatal Research Department will also be notified via email at the beginning of each week.

An Epic order will be placed by provider specifying "Foley balloon under tension" or "Foley balloon No Tension" according to the randomization assignment.

Subjects under treatment conditions before this time will be included as part of the treatment block assignment at the time of inclusion and will not be allowed to cross over. The subject will be included in the analysis by intention-to-treat once the randomization assignment has been made.

The cluster randomized trial design is such that each week, the chosen method of induction of labor in subjects meeting inclusion criteria is randomized to either the Tension standard of care (control group) or No Tension standard of care (study group). All subjects who would meet inclusion criteria for foley balloon induction of labor will be participants in the study. The two methods of induction being compared are currently accepted and practiced standards used for women with an unfavorable cervix who

require induction of labor. The risks and benefits of induction of labor will be discussed with each patient prior to administration and consent for delivery obtained, consistent with the current standard of care on Labor and Delivery at *UTMB*.

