The primary risk of participation in the study is breach of confidentiality. The waiver of consent for research is appropriate because no contact between the study team and subjects will take place outside of standard clinical care. All subjects will receive one of two standards of care, which are currently selected per providers choice for placing the Foley balloon either under tension (tubing taped to thigh) or without tension (tubing hangs free). We feel this study is of minimal risk, as subjects would normally receive this standard of care through an uncontrolled randomized process of provider's choice, which inconsistently varies between tension vs. no tension. Randomizing the method of tension versus no tension in a controlled process, will allow data to be effectively analyzed to assess if one method is best for subjects. Both methods of induction utilized are approved by the American College of Obstetricians and Gynecologists, and it is not currently known if one method is inferior to the other.

Additionally, we will be obtaining written consent from all providers that practice in our unit, relinquishing the standard of care method of Foley balloon placement with tension or no tension to a controlled randomized process before initiation of the trial. The provider consent document is attached in the IRB application.

The cluster randomized trial design is such that each week, the chosen method of induction of labor in subjects meeting inclusion criteria is randomized to either:

- Foley balloon with tension which is current standard of care (control group)
- Foley balloon without tension (tension free) which is also a current standard of care (study group).

To summarize:

- A waiver of patient consent for research is requested
- No subjects will be consented for research

- Written medical consent for delivery will be obtained from all subjects per standard of care
- The risks and benefits of induction of labor will be discussed with each patient prior to obtaining medical consent for delivery, which is consistent with the current standard of care.
- In addition subjects will be verbally informed the type of labor induction they will receive, (which is also consistent with current standard of care):
 - Foley balloon with tension (tubing taped to thigh)
 - o Foley balloon without tension (tubing hangs free)
- Written research consent will be obtained from all providers to follow weekly randomization of tension vs. no tension

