4.3. Placement of Foley Balloon

The control group will undergo induction of labor by placement of a transcervical Foley balloon, which is standard of care at our institution. A Foley balloon will be introduced into the cervix either manually or under direct visualization with a sterile speculum exam based on provider preference and training. The balloon will be filled with 60 ml of sterile 0.9% NaCl. Proper placement will be confirmed manually. The balloon tubing will be pulled to create tension and will then be taped to the patient's inner thigh. The foley balloon will be left in place on tension for at least 12 hours, and no longer than 24 hours. Balloon tension will be periodically assessed, and tension reapplied if needed.

The study group will undergo induction of labor by placement of a transcervical Foley balloon as the control group. A Foley balloon is introduced into the cervix either manually or under direct visualization as the control group but the foley will not be taped or under tension. The balloon tubing will be left free of tension and will hang freely.

Additional information regarding management of the foley balloon in both the study and control group:

- Placement of the Foley balloon will be performed by the managing obstetrical team.
- The Foley balloon will be left in place for at least 12 hours, and no longer than 24 hours.
- Balloon will be assessed close to 12 hours following placement in all participants.
- The balloon may be assessed prior to the 12 hours for a variety of reasons including, for example, patient request, changes in fetal heart tracing, increased reported pain, and spontaneous rupture of membranes. The reason for checking prior to twelve hours will be documented.
- Following expulsion or removal at 12 hours, sterile vaginal exam will be performed. Patient will then undergo standard intrapartum care.
- If cervix remains unfavorable after extraction of the foley balloon at 12 hours (< 3cm and at most 60% effaced), a second Foley balloon will be used in this case for a maximum of 12 hrs. No crossover will be allowed. In other words, a second Foley balloon will be placed in the same manner as the first assignment arm.
- If the Foley balloon is unable to be placed in either insertion technique, a prostaglandin agent for cervical ripening may be used and insertion of the mechanical dilator can be re-attempted at a later time, as is the standard of care at our institution. No cross over will be allowed.

Visit#2

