
4.4. Additional Baseline Procedures

- Routine intrapartum care will be provided by the patient's managing obstetric team.
- Trained and experienced study team will be responsible for all research data abstraction.
- The PI and faculty sponsor will review and validate the diagnosis for all subjects identified to have the primary outcomes. If there is uncertainty, a faculty sponsor will review the chart, discuss with the study team as needed, and make a final determination regarding the outcome.

- Maternal outcomes will be assessed following delivery.
- Data collection forms will be used during these processes and charts will be reviewed up to 30 days postpartum. We will collect demographic data, as well as data related to the patient's intrapartum course, delivery, and immediate postpartum period while inpatient.
- Subjects' participation will end following delivery.

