4.9 Secondary Outcomes

- Request for IV/PO pain medications or epidural placement following placement of Foley balloon transcervical dilator during cervical ripening period
- Time of artificial rupture of membranes
- Incidence of malpresentation following removal of foley balloon
- Incidence of primary cesarean delivery
- Incidence of postpartum hemorrhage
- Chorioamnionitis (also known as "IAI," or "triple I"):
 - O A **presumptive diagnosis** of IAI (suspected triple I) can be made in women with:
 - Fever –≥39.0°C [102.2°F] or 38.0°C [100.4°F] to 38.9°C [102.02°F] on two occasions 30 minutes apart, without another clear source PLUS one or more of the following:
 - Baseline fetal heart rate >160 beats/min for ≥10 minutes, excluding accelerations, decelerations, and periods of marked variability
 - Maternal white cell count >15,000/mm3 in the absence of corticosteroids and ideally showing a left shift (bandemia)
 - Purulent-appearing fluid coming from the cervical os visualized by speculum examination
 - O A **confirmed diagnosis** of IAI can be made in women with:
 - All of the above PLUS one or more of the following objective laboratory findings:
 - Positive Gram stain of amniotic fluid
 - Low glucose level in amniotic fluid
 - Positive amniotic fluid culture
 - High white cell (WBC) count in amniotic fluid in the absence of a bloody tap
 - Histopathologic evidence of infection or inflammation or both in the placenta, fetal membranes, or the umbilical cord vessels (funisitis)
- Endometritis must meet the following criteria:
 - O Infection occurs within 30 days after the operative procedure AND
 - o Infection presumed to involve the uterus AND
 - O Patient has at least one of the following:
 - Purulent drainage from a drain that is placed through a stab wound into the abdomen or pelvis
 - Organisms isolated from an aseptically-obtained culture of fluid or tissue in the organ / space
 - An abscess or other evidence of infection involving the abdomen or pelvis that is found on direct examination, during re-operation, or by histopathologic or radiologic examination
- Neonatal infection, defined as sepsis, fever, positive cultures, or a suspicious clinical course that warranted treatment with antibiotics

- APGAR scores
- NICU admission rates
- Neonatal hospital length of stay

5. Criteria for Inclusion of Subjects:

- Women >18 and <50
- Term induction of labor
- Nulliparous
- Vertex
- Singleton

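### The study team that abstracts all outcomes is told each week's arm, so the secondary outcomes with a judgment element are read unmasked, for no stated purpose

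*Combined protocol and SAP*

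**What the plan says.** Section 4.2 (Labor and Delivery Unit/Staff) announces the week's arm to nurses and providers, and tags work stations and patient doors. It then extends the disclosure to the research side: "All study team in the Perinatal Research Department will also be notified via email at the beginning of each week". It also says: "A notification will also be placed at the work station of the study team".

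Section 4.4 assigns data extraction: "Trained and experienced study team will be responsible for all research data abstraction". It adds a review step: "The PI and faculty sponsor will review and validate the diagnosis for all subjects identified to have the primary outcomes". If there is doubt, "a faculty sponsor will review the chart, discuss with the study team as needed, and make a final determination regarding the outcome".

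Delivery of the technique lies elsewhere. Section 4.3 says: "Placement of the Foley balloon will be performed by the managing obstetrical team". The waiver justification in section 4.1 says that "no contact between the study team and subjects will take place outside of standard clinical care". Under section 7 the data source is the electronic record, and section 4.7 names both the mother's and the neonate's charts.

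No section masks an abstractor or reviewer, and none says why abstractors should know the arm.

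**The concern.** Clinicians and nurses in this trial cannot be blinded. Those who later read the charts need not share that knowledge, at least not fully. Here the plan actively gives them the arm.

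Three secondary outcomes in section 4.9 call for some interpretation: suspected intraamniotic infection, endometritis and neonatal infection. These outcomes would count against either technique, and section 1 states a directional hypothesis in favor of tension. If unclear charts are read even slightly differently by arm, the comparison shifts, in a direction that cannot be predicted. The multilevel regression in section 12 cannot correct this, because the error sits in the recorded outcome.

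**Working it through.** **1. Who is told and who reads.** Section 4.2 informs all study team in the research department, by email and by posted notice. Section 4.4 has the study team abstract all research data. As written, the abstractors are among those told. The managing obstetrical team places the balloon, so abstraction itself does not require the arm.

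**2. How much judgment each outcome leaves (section 4.9).**

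- *Suspected intraamniotic infection.* Fever has numeric thresholds, and at least one further sign is needed (fetal heart rate, white-cell count or purulent fluid). The open element is whether something else explains the fever.
- *Endometritis.* The presumption that the uterus is the site is joined by AND to at least one listed finding. The open elements are that presumption and the broad wording of the third finding.
- *Neonatal infection.* The limbs are joined by OR, and the last is "a suspicious clinical course that warranted treatment with antibiotics". It can suffice alone. Giving antibiotics is a recorded act of the treating clinician; calling the course suspicious is a matter of reading.
- *Primary outcome (section 4.8).* Elapsed time from placement to delivery, taken from recorded times, with little to interpret.

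**3. Routes by which an abstractor learns the arm.** (a) The email and posted notice. (b) The provider's Epic order, which names the technique (section 4.2). (c) The calendar: the arm is constant within a week, so anyone who knows the week's arm can generally infer it from dates, including those in a neonate's chart that never mentions tension. One week covers about 265/17 = 15.6 women (section 12 addendum). Closing route (a) alone therefore does not mask anyone who opens maternal charts.

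**4. The plan's own figures.** Section 12 gives means of 1053.399 and 1316.74 minutes, SD 535.73, 10 per cluster, rho 0.1, 80% power and two-sided alpha 0.05.

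- Difference: 1316.74 − 1053.399 = 263.341.
- n per arm without clustering: 2 × (535.73 × (1.960 + 0.842) / 263.341)² = 64.97.
- Design effect: 1 + 9 × 0.1 = 1.9, and 64.97 × 1.9 = 123.4.
- 123.4 / 10 = 12.34, rounded up to 13 clusters, or 130 per arm. This matches the plan.
- Total: 265/17 × 26 = 405.3, which matches 405.

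None of these figures depends on who knows the arm.

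**5. Size of a possible bias.** If a share *b* of charts is borderline, and these are called positive *d* more often in one arm, the false difference is *b* × *d*. The documents give neither quantity and no event rate. As pure assumption, take a true rate of 8% in both arms, *b* = 10% and *d* from 0 to 20 points:

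- *d* = 0: no bias.
- *d* = 10 points: 0.08 + 0.10 × 0.10 = 0.09, ratio 0.09/0.08 = 1.125.
- *d* = 20 points: 0.08 + 0.10 × 0.20 = 0.10, ratio 0.10/0.08 = 1.25.

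With 405/2 = 202.5 women per arm, the last case is about 4 women (202.5 × 0.02 = 4.05). The standard error of that difference, ignoring clustering, is √((0.08 × 0.92 + 0.10 × 0.90)/202.5) = 0.028, or 2.8 points. Even the largest assumed shift, 2 points, is below one standard error.

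**6. Timing.** Recruitment began on June 6, 2022, and 17 weekly clusters were complete by October 3, 2022. That is 17 weeks, so the clusters ran consecutively. At that pace 26 clusters end in early December 2022. The current version is dated 02/28/2023, so by inference most or all notices had already gone out.

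**The case against.** Several points on the other side are strong.

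- *Review.* A reader might infer that the whole informed team adjudicates the infection outcomes. Section 4.4 does not say so. Review is by the PI and faculty sponsor and is stated only for the primary outcome. For the secondary outcomes only abstraction is at issue. This stands.
- *Purpose.* A reader might infer that telling the team serves no end at all. The documents do not show that. They do not say who announces the arm or places the tags, the PI answers staff questions, and section 4.1 excludes contact only outside standard care, so some members may also be treating clinicians. What remains is narrower: no purpose is stated for telling those who abstract.
- *Epic order.* The order discloses the arm anyway, and placement time and analgesia during ripening lead an abstractor to that part of the chart. This stands, and it rules out any remedy that only stops the email. It also rules out having one person read maternal delivery and infection data as well as neonatal charts, since that person would learn the week's arm from the mother.
- *Definitions.* The infection criteria are partly objective, and treating clinicians who know the arm decide on antibiotics. This stands; it limits what masking can achieve but does not remove the judgment elements in step 2.
- *Size.* The inputs in step 5 are hypothetical, and a consequential effect is not demonstrated. This stands.

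**Conclusion.** The concern holds for the abstraction of suspected intraamniotic infection, endometritis and neonatal infection. The plan tells the people who abstract these outcomes which arm each week is in, masks none of them and gives no reason. This is a stated practice that adds an avoidable risk of bias, not merely a missing detail.

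It does not extend to the primary outcome in any material way. A reader might infer that the main comparison is compromised, but times of placement and delivery leave little to interpret, and the power calculation is unaffected.

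The size of any bias cannot be estimated from the documents; the range in step 5 rests wholly on assumed inputs and starts at zero. The conclusion assumes that the abstractors are among the study team members who receive the notices, as sections 4.2 and 4.4 read together imply. It is worth acting on because the remedy is cheap, not because harm has been shown.

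**What to change.** - Limit the weekly email and work-station notice to team members who run the allocation on the unit.
- Leave arm off the outcome form. At analysis, merge it from the randomization list by date of inclusion, which is how section 4.2 already assigns women present at a change of week.
- Using existing staff, have neonatal outcomes abstracted from the neonate's chart by a member who did not receive the notices and does not read maternal charts.
- Have borderline maternal infection cases classified from extracts without the Foley order, arm or calendar dates.
- For weeks whose notices have already been sent, apply the masked extracts to outcomes not yet abstracted, or to a re-read of borderline cases. Report that the remaining abstraction was unmasked.

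The cost is a little extra work in preparing extracts and dividing the abstraction. Masking of maternal outcomes will be only partial, and bias in care or charting by clinicians who know the arm is not removed.

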4.3. Placement of Foley Balloon

The control group will undergo induction of labor by placement of a transcervical Foley balloon, which is standard of care at our institution. A Foley balloon will be introduced into the cervix either manually or under direct visualization with a sterile speculum exam based on provider preference and training. The balloon will be filled with 60 ml of sterile 0.9% NaCl. Proper placement will be confirmed manually. The balloon tubing will be pulled to create tension and will then be taped to the patient's inner thigh. The foley balloon will be left in place on tension for at least 12 hours, and no longer than 24 hours. Balloon tension will be periodically assessed, and tension reapplied if needed.

The study group will undergo induction of labor by placement of a transcervical Foley balloon as the control group. A Foley balloon is introduced into the cervix either manually or under direct visualization as the control group but the foley will not be taped or under tension. The balloon tubing will be left free of tension and will hang freely.

Additional information regarding management of the foley balloon in both the study and control group:

- Placement of the Foley balloon will be performed by the managing obstetrical team.
- The Foley balloon will be left in place for at least 12 hours, and no longer than 24 hours.
- Balloon will be assessed close to 12 hours following placement in all participants.
- The balloon may be assessed prior to the 12 hours for a variety of reasons including, for example, patient request, changes in fetal heart tracing, increased reported pain, and spontaneous rupture of membranes. The reason for checking prior to twelve hours will be documented.
- Following expulsion or removal at 12 hours, sterile vaginal exam will be performed. Patient will then undergo standard intrapartum care.
- If cervix remains unfavorable after extraction of the foley balloon at 12 hours (< 3cm and at most 60% effaced), a second Foley balloon will be used in this case for a maximum of 12 hrs. No crossover will be allowed. In other words, a second Foley balloon will be placed in the same manner as the first assignment arm.
- If the Foley balloon is unable to be placed in either insertion technique, a prostaglandin agent for cervical ripening may be used and insertion of the mechanical dilator can be re-attempted at a later time, as is the standard of care at our institution. No cross over will be allowed.

Visit#2

4.4. Additional Baseline Procedures

- Routine intrapartum care will be provided by the patient's managing obstetric team.
- Trained and experienced study team will be responsible for all research data abstraction.
- The PI and faculty sponsor will review and validate the diagnosis for all subjects identified to have the primary outcomes. If there is uncertainty, a faculty sponsor will review the chart, discuss with the study team as needed, and make a final determination regarding the outcome.

- Maternal outcomes will be assessed following delivery.
- Data collection forms will be used during these processes and charts will be reviewed up to 30 days postpartum. We will collect demographic data, as well as data related to the patient's intrapartum course, delivery, and immediate postpartum period while inpatient.
- Subjects' participation will end following delivery.

4.5. Study visits / Follow-up

No extra postpartum follow-up visits will be performed.

4.6. Withdrawals

[figure not shown]
Subjects who withdraw from the study will be excluded from further follow-up. Outcomes ascertained up until the time of withdrawal will be reported in intention-to-treat fashion. The patient will be withdrawn from the study if she wishes to discontinue participation. If any of the exclusion criteria listed above are met, or condition changes that leads to inclusion criteria not being met anymore, data collection will be terminated, and the patient will be withdrawn from the study.

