Recruitment: Subjects will not be recruited, however, we will include records of all nulliparous pregnant subjects admitted to L&D for scheduled induction of labor at term who have had a decision made by their managing clinical team to place a transcervical foley balloon for purposes of mechanical dilation who met inclusion and exclusion criteria listed below.

2 V4.1 Protocol Version Date: 02/28/2023

Screening: Subject records will be screened and included if they met inclusion and exclusion criteria at the time a decision to place a transcervical foley balloon with or without tension under the randomized sequence for purposes of mechanical dilation was made in labor and delivery.

Consenting process: Subjects will not be consented; we are requesting a waiver of patient consent. However, we will be obtaining written consent from all faculty providers that practice in our unit, relinquishing the standard of care method for placement of Foley balloon with tension versus no tension to a controlled randomized process before initiation of the trial. The provider consent form is attached in the application. Subjects will not be consented for the study; however, subjects will be verbally informed about the methods used for induction of labor. Providers placing the Foley balloon will obtain verbal consent for labor induction with Foley balloon with tension or without tension, which is the current standard of care. Written consent to participate in this study will be obtained from the faculty who agree to allow their patients to participate in this research protocol. Providers may withdraw individual patients from the study if the provider no longer deems that participation is in the best interest of the individual.

Justification of waiver:

Consent for research will not be obtained as this study involves two standards of care that are currently being performed at UTMB. A waver of informed consent will be submitted with the IRB application. However, we will be obtaining written consent from all providers (see attached document and more information below).

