- Plan for Foley balloon placement by the managing obstetrics team
- Cervical exam less than 3 cm dilated and less than or equal to 60% effaced

6. Criteria for Exclusion of Subjects:

- Patient unwilling or unable to provide verbal consent
- Fetal demise or major congenital anomaly
- Preterm (<37 0/7weeks)
- Multiple gestation
- Previous uterine surgery
- Abnormal placentation
- Malpresentation
- Magnesium infusion for preeclampsia with severe features
- Prelabor rupture of membranes
- Fetal growth restriction
- Non-reassuring fetal heart rate tracing prior to inclusion

7. Sources of Research Material: Electronic medical chart / records

8. Potential Risks:

No significant adverse effects are expected with the use of transcervical Foley balloons for mechanical dilation. Foley balloons are the standard of care for induction of labor at UTMB. The most significant risks are vaginal bleeding due to cervical trauma and incidental rupture of membranes, as well as pain or discomfort with placement. The patient will undergo inpatient induction of labor, so any adverse reaction would be promptly detected and addressed.

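### Section 4.6 ends data collection when a woman stops meeting the entry criteria, with no time limit, so women already assigned can be lost before delivery, contrary to intention-to-treat.

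*Combined protocol and SAP*

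**What the plan says.** Section 4.6 (Withdrawals) covers two events: an exclusion criterion being met, or the case where "condition changes that leads to inclusion criteria not being met anymore, data collection will be terminated, and the patient will be withdrawn". It gives no time window. It also says that withdrawn women have no further follow-up and that outcomes recorded before withdrawal are kept on an intention-to-treat basis.

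Other sections point the other way:

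- Section 4.1 (Screening): records are "included if they met inclusion and exclusion criteria at the time a decision to place a transcervical foley balloon" is made.
- Section 4.2: "The subject will be included in the analysis by intention-to-treat once the randomization assignment has been made". Section 12 repeats intention-to-treat.
- Section 4.3, after balloon expulsion or removal: "Patient will then undergo standard intrapartum care".
- Section 4.4: "charts will be reviewed up to 30 days postpartum".
- Section 4.9 lists as a secondary outcome "Incidence of malpresentation following removal of foley balloon", while Section 6 lists malpresentation as an exclusion criterion without a date.
- Section 6 dates only one criterion: "Non-reassuring fetal heart rate tracing prior to inclusion".
- Section 12 sizes the trial on the assumption that every outcome is ascertained.

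Section 4.1 adds a separate route out: "Providers may withdraw individual patients from the study if the provider no longer deems that participation is in the best interest of the individual".

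**The concern.** Allocation is by week for the whole unit, so a woman is assigned as soon as she is included. A rule that then removes her because her condition has changed is a post-randomization exclusion. Some of the triggers can follow from the balloon or from the labor it starts, so removal may be related to both treatment and outcome.

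Keeping outcomes up to withdrawal does not repair this. The primary outcome runs from balloon placement to delivery and is known only at delivery. Cesarean, hemorrhage and the neonatal outcomes also come later.

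Staff know the week's assignment (Section 4.2), and the treating provider can also withdraw a patient, so losses could differ between arms. For any woman removed in this way, the promised intention-to-treat analysis cannot be completed.

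**Working it through.** **1. Is this only a screening rule?** The wording describes a woman who met the criteria and no longer does, and data collection that has begun and is stopped. Both fit a woman already included. Nothing in the section confines the rule to the time before the placement decision.

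**2. Which criteria could trigger it after placement?**

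| Criterion | Dated? | Can arise after placement? | Addressed elsewhere? |
|---|---|---|---|
| Malpresentation / vertex | No | Yes | Yes: a secondary outcome (4.9), in direct conflict with 4.6 |
| Magnesium for severe preeclampsia | No | Yes | No |
| Prelabor rupture of membranes | No | Arguable | 4.3 treats rupture after placement only as a reason to check the balloon |
| Cervix under 3 cm and at most 60% effaced | No | Yes, it is the aim of ripening | 4.3 continues care, so not meant as a trigger |
| Non-reassuring fetal heart rate | Yes | Not applicable | Limited to before inclusion |

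The point rests on the first two rows.

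**3. The plan's own sample size (Section 12).** Inputs: means 1053.399 and 1316.74 min, SD 535.73, rho 0.1, 10 per cluster, 80% power, two-sided alpha 0.05.

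- Target difference: 1316.74 − 1053.399 = 263.34 min.
- Per arm without clustering: 2 × (535.73 × (1.960 + 0.842) / 263.34)² = 64.97.
- Design effect: 1 + 9 × 0.1 = 1.9, giving 123.4 per arm, or 12.34 clusters, rounded up to 13 (130 per arm). This matches the plan.
- The total of 405 also follows: 265 / 17 × 26 = 405.3.

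**4. Power lost through smaller numbers.** SE = 535.73 × √(2 × (1 + (m − 1) × 0.1) / (13 × m)), with m women per cluster. Power = Φ(263.34 / SE − 1.96).

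| m | Meaning | SE (min) | Power |
|---|---|---|---|
| 10 | original plan | 91.6 | 82.0% |
| 9 | 10% loss | 94.0 | 80.0% |
| 15.58 | 405 / 26 | 83.5 | 88.4% |
| 14.02 | 10% loss | 85.1 | 87.1% |

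The loss of power is small.

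**5. Bias.** If a share p of an arm is withdrawn and would have averaged x min longer than those retained, the observed arm mean is too low by p × x. The difference therefore shifts by (p₂ − p₁) × x when x is the same in both arms. The documents give neither p nor x, so the values below are assumed.

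- Equal p and x in both arms: shift 0.
- 5% vs 10%, x = 1 SD: 0.05 × 535.73 = 26.8 min, which is 26.8 / 263.34 = 10.2% of the target.
- 5% vs 10%, x = 2 SD: 0.05 × 1071.46 = 53.6 min, or 20.3%.
- 5% vs 15%, x = 1 SD: 0.10 × 535.73 = 53.6 min. A true 263.3 would be observed as 209.8 if the no-tension arm loses more.

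**6. Type I error under the same shifts.** Average loss of 7.5% gives m = 15.58 × 0.925 = 14.41 and SE 84.7. With s = shift / SE, error = Φ(−1.96 + s) + Φ(−1.96 − s).

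- Shift 26.8: s = 0.316, error about 6.2%.
- Shift 53.6: s = 0.633, error about 9.7%.

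The SD and rho are held at their planning values throughout.

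**The case against.** The best defense is that the protocol, read as a whole, treats the entry criteria as baseline criteria. Section 4.1 fixes eligibility at the placement decision, Section 4.3 continues care after the balloon, and Section 4.9 expects malpresentation to be recorded after removal. On that reading Section 4.6 only lacks the words confining it to the time before placement. This may well be what was intended. But the sentence as written tells an abstractor to stop, and malpresentation being listed both as an outcome and as an undated exclusion criterion is the contradiction, not its resolution. No other section deals with magnesium started later.

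Other points stand in part:

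- Nothing in the documents shows that any woman was withdrawn under this rule, and the rates in the illustration have no source. A 2 SD gap (1,071 min) exceeds the whole control mean (1,053 min) and is an extreme case.
- No direction by arm can be argued from the documents.
- Section 4.8 speaks of vaginal delivery and Section 12 of delivery. For a woman delivered by cesarean, what is lost on the primary outcome depends on resolving that difference. The other later outcomes are lost either way.
- Provider withdrawal is a different rule from loss of eligibility. It is relevant here because it too can remove assigned women.
- A figure under Section 4.6 and the flow diagram could not be read in the copy reviewed. Neither could cancel an explicit sentence.

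**Conclusion.** The concern holds. Section 4.6 contradicts the eligibility time point in Section 4.1 and the intention-to-treat commitments in Sections 4.2 and 12, and it undercuts the complete ascertainment on which the sample size rests. It should be fixed, and that conclusion rests on the text rather than on the figures.

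The size is unknown. It is zero if the rule was never applied after assignment, or if loss and prognosis were equal across arms. A difference of 5 percentage points in withdrawal, with withdrawn women 1 to 2 SD slower, would shift the comparison by 27 to 54 min (10% to 20% of the target) and put two-sided type I error at about 6.2% to 9.7%. The shift could favor either arm. Reduced numbers alone cost at most about 2 points of power at 10% loss.

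**What to change.** In Section 4.6:

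- State that the entry criteria apply once, at the decision to place the Foley.
- Delete the sentence ending data collection for later changes, or limit it to ineligibility on facts that pre-date that decision.
- Continue chart abstraction to delivery and through the existing 30-day review for every included woman, including any whom a provider withdraws, and analyze her by her assigned week.
- Reserve the end of data collection for a woman's own objection.
- Re-abstract the charts of any women already withdrawn under the rule, and report number and reason by arm.

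The sponsor should also reconcile the provider-withdrawal text in Section 4.1 with the no-crossover text in Section 4.3. No treatment rule is proposed here.

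The cost is small: a wording change, plus abstraction from records already reviewed to 30 days under a requested waiver of patient consent. The sample size is unaffected. The addendum reports 17 of 26 clusters and 265 women complete by October 2022. With weekly clusters from June 2022 and no pauses, all 26 would have finished around December 2022, before this version's date of February 2023. In practice the remedy may therefore be mostly chart recovery and reporting, and the IRB may need to confirm that the waiver covers it.
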